10.6.2. Age-Specific Kidney Function Calculation Recommendations

10.6.2.1. Adults (18 Years and Above)—2021 CKD-EPI Equations

eGFR (mL/min/1.73m²)^[7]

2021 CKD-EPI Screat Only	Screat (mg/dL)	Scys (mg/L)	Recommended eGFR Equation
Female	if < 0.7	NA	$eGFR = 143 \times (Screat/0.7)^{-0.241} \times (0.9938)^{Age}$
Female	if > 0.7	NA	$eGFR = 143 \times (Screat/0.7)^{-1.200} \times (0.9938)^{Age}$
Male	if < 0.9	NA	$eGFR = 142 \times (Screat/0.9)^{-0.302} \times (0.9938)^{Age}$
Male	if > 0.9	NA	$eGFR = 142 \times (Screat/0.9)^{-1.200} \times (0.9938)^{Age}$
2021 CKD-EPI Screat-Scys Combined	Screat (mg/dL)	Scys (mg/L)	Recommended eGFR Equation
Female	if < 0.7	if < 0.8	$eGFR = 130 \times (Screat/0.7)^{-0.219} \times (Scys/0.8)^{-0.323} \times (0.9961)^{Age}$
Female	if < 0.7	if > 0.8	$eGFR = 130 \times (Screat/0.7)^{-0.219} \times (Scys/0.8)^{-0.778} \times (0.9961)^{Age}$
Female	if > 0.7	if < 0.8	$eGFR = 130 \times (Screat/0.7)^{-0.544} \times (Scys/0.8)^{-0.323} \times (0.9961)^{Age}$
Female	if > 0.7	if > 0.8	$eGFR = 130 \times (Screat/0.7)^{-0.544} \times (Scys/0.8)^{-0.778} \times (0.9961)^{Age}$
Male	if < 0.9	if < 0.8	$eGFR = 135 \times (Screat/0.9)^{-0.144} \times (Scys/0.8)^{-0.323} \times (0.9961)^{Age}$
Male	if < 0.9	if > 0.8	$eGFR = 135 \times (Screat/0.9)^{-0.144} \times (Scys/0.8)^{-0.778} \times (0.9961)^{Age}$
Male	if > 0.9	if < 0.8	$eGFR = 135 \times (Screat/0.9)^{-0.544} \times (Scys/0.8)^{-0.323} \times (0.9961)^{Age}$
Male	if > 0.9	if > 0.8	$eGFR = 135 \times (Screat/0.9)^{-0.544} \times (Scys/0.8)^{-0.778} \times (0.9961)^{Age}$

10.6.3. Kidney Function Calculation Tools

The sponsor has provided the following resources to investigational sites when required to calculate age-specific kidney function at Screening, Baseline, and post-Baseline visits. Site calculations of kidney function can be performed manually, using the age appropriate formulae (see Section 10.6.2) and can use recommended online kidney function calculators to reduce the likelihood of a calculation error.

The United States National Kidney Foundation Online Calculators.

- Adults (18 years and above) - 2021 CKD-EPI Creatinine Online Calculator (eGFR): https://www.kidney.org/professionals/KDOQI/gfr_calculator

Investigational sites are responsible to ensure that the accurate age-specific equation is selected and that the correct units for serum creatinine (mg/dL only), serum cystatin C (mg/L only), total body weight (kg only), and age (years). Investigators are expected to (i) review and confirm correctness of the kidney function calculation results and (ii) evaluate the calculated value within the context of historical information available to them in the participant's medical record. Investigators are responsible for the clinical oversight of the participant eligibility process, kidney function calculation, and dose selection and adjustments per study protocol. Investigators are encouraged to direct questions or uncertainties regarding kidney function and dosing to the Pfizer Clinical Team and Medical Monitor, if needed.

10.6.4. Adverse Event Grading for Kidney Safety Laboratory Abnormalities

AE grading for decline in kidney function (ie, eGFR or eCrCl) will be according to Kidney Disease: Improving Global Outcomes (KDIGO) criteria for adult participants.

KDIGO criteria grade (G)	Study Population	G1	G2	G3	G4	G5
Decreased Kidney Function due to either Acute or Chronic Kidney Injury	Adult participants eGFR (mL/min/1.73m ²)	≥90	≥60 to 89	30 to 59	15 to 29	<15

KDIGO albuminuria (A) criteria	A1	A2	A3
Albumin-to-creatinine ratio (ACR)	<30 mg/g OR <3 mg/mmol	30 to 300 mg/g OR 3 to 30 mg/mmol	>300 mg/g OR >30 mg/mmol

10.7. Appendix 7: ECG Findings of Potential Clinical Concern

ECG Findings That May Qualify as AEs

Marked sinus bradycardia (rate <40 bpm) lasting minutes.New PR interval prolongation >280 ms.New prolongation of QTcF to >480 ms (absolute).New prolongation of QTcF by >60 ms from baseline.New-onset atrial flutter or fibrillation, with controlled ventricular response rate: ie, rate <120 bpm.New-onset type I second-degree (Wenckebach) AV block of >30-second duration.Frequent PVCs, triplets, or short intervals (<30 seconds) of consecutive ventricular complexes.
ECG Findings That May Qualify as SAEs

QTcF prolongation >500 ms.Absolute value of QTcF > 450 ms AND QTcF change from baseline >60 ms.New ST-T changes suggestive of myocardial ischemia.New-onset LBBB (QRS complex >120 ms).New-onset right bundle branch block (QRS complex >120 ms).Symptomatic bradycardia.Asystole
In awake, symptom-free participants in sinus rhythm, with documented asystolic pauses ≥ 3 seconds or any escape rate <40 bpm, or with an escape rhythm that is below the AV node;In awake, symptom-free participants with atrial fibrillation and bradycardia with 1 or more asystolic pauses of at least 5 seconds or longer.Atrial flutter or fibrillation, with rapid ventricular response rate: rapid = rate >120 bpm.

- Sustained supraventricular tachycardia (rate >120 bpm) (“sustained” = short duration with relevant symptoms or lasting >1 minute).
- Ventricular rhythms >30 seconds’ duration, including idioventricular rhythm (HR <40 bpm), accelerated idioventricular rhythm (HR >40 bpm to <100 bpm), and monomorphic/polymorphic ventricular tachycardia (HR >100 bpm [such as torsades de pointes]).
- Type II second-degree (Mobitz II) AV block.
- Complete (third-degree) heart block.

ECG Findings That Qualify as SAEs

- Change in pattern suggestive of new myocardial infarction.
- Sustained ventricular tachyarrhythmias (>30-seconds duration).
- Second- or third-degree AV block requiring pacemaker placement.
- Asystolic pauses requiring pacemaker placement.
- Atrial flutter or fibrillation with rapid ventricular response requiring cardioversion.
- Ventricular fibrillation/flutter.
- At the discretion of the investigator, any arrhythmia classified as an adverse experience.

The major events of potential clinical concern listed above are recommended as “alerts” or notifications from the core ECG laboratory to the investigator and Pfizer study team, and not to be considered as all-inclusive of what is to be reported as AEs/SAEs.

10.8. Appendix 8: Prohibited Concomitant Medications That May Result in DDI

The prohibited concomitant medications listed below and antibiotics should not be taken with sisunatovir for the period of time at least equal to 5 half-lives plus 14 days preceding the first dose of study intervention, and throughout the conduct of the study.

The Pfizer study team is to be notified of any prohibited medications taken during the study. After consulting with the sponsor, the investigator will make a judgment on the ongoing participation of any participant with prohibited medication use during the study.

This list of drugs prohibited for potential DDI concerns with the IMP may be revised during the course of the study with written notification from the sponsor to include or exclude specific drugs or drug categories for various reasons (eg, emerging DDI results for the IMP, availability of new information in literature on the DDI potential of other drugs) if the overall benefit:risk assessment is not impacted or if the changes do not significantly impact the safety of participants or the scientific value of the trial.

Strong and moderate CYP3A4 and P-gp inhibitors or inducers are prohibited, as these medications may have meaningful impact on the pharmacokinetics of sisunatovir.

Sisunatovir is a CYP3A4 inhibitor and therefore sensitive and narrow therapeutic index CYP3A4 substrates are also prohibited in this study. Since based on in vitro data sisunatovir may be a weak inhibitor of CYP2B6, sensitive narrow TI substrates of CYP2B6 are excluded.

Sisunatovir also may be an inhibitor of OCT1 and MATE1 transporters; therefore, sensitive substrates of these transporters are excluded.

Although not all-inclusive, a list of medications that are prohibited in this study is provided below. Site staff should consult with the sponsor or designee with any questions regarding potential DDI.

Investigators should consult the product label for any other medication used during the study for information regarding medication that is prohibited for concomitant use.

Prohibited Concomitant Medications

CYP3A Inhibitors		CYP3A Inducers	
Moderate	Strong	Moderate	Strong
Aprepitant	Boceprevir	Bosentan	Apalutamide
Ciprofloxacin	Cobicistat	Efavirenz	Carbamazepine
Conivaptan	Danoprevir	Etravirine	Enzalutamide
Crizotinib	Dasabuvir	Phenobarbital	Mitotane
Cyclosporine	Elvitegravir	Primidone	Phenytoin
Diltiazem	Indinavir		Rifampin
Dronedarone	Itraconazole		St. John's wort
Erythromycin	Ketoconazole		
Fluconazole	Lopinavir		
Fluvoxamine	Paritaprevir		

Imatinib	Ombitasvir		
Tofisopam	Posaconazole		
Verapamil	Ritonavir		
	Saquinavir		
	Telaprevir		
	Tipranavir		
	Telithromycin		
	Troleandomycin		
	Voriconazole		
Sensitive CYP3A Substrates		CYP3A Substrates with Narrow Therapeutic Index	
Alfentanil	Lovastatin	Alfentanil	
Atorvastatin	Lurasidone	Astemizole	
Avanafil	Maraviroc	Cisapride	
Budesonide	Midazolam	Cyclosporine	
Buspirone	Naloxegol	Dihydroergotamine	
Darifenacin	Nisoldipine	Ergotamine	
Darunavir	Quetiapine	Fentanyl	
Dasatinib	Sildenafil	Pimozone	
Dronedarone	Simvastatin	Quinidine	
Ebastine	Sirolimus	Sirolimus	
Eletriptan	Tacrolimus	Tacrolimus	
Eplerenone	Ticagrelor	Terfenadine	
Everolimus	Tolvaptan		
Ibrutinib	Tipranavir		
Indinavir	Triazolam		
Felodipine	Vardenafil		
Lomitapide	Fentanyl		
Sensitive MATE1 Substrates			
Metformin			
Sensitive CYP2B6 Substrates		CYP2B6 Substrates with Narrow Therapeutic Index	
Velpatasvir		Cyclophosphamide	
P-gp Inhibitors		P-gp Inducers	
Atazanavir	Lopinavir	Apalutamide	
Boceprevir	Lumacaftor	Atazanavir	
Cobicistat	Mifepristone	Fosamprenavir	
Conivaptan	Nelfinavir	Lopinavir	
Cyclosporine	Ombitasvir and paritaprevir and ritonavir and dasabuvir	Rifampin	
Darunavir	Posaconazole	St. John's wort (hypericum perforatum) extract	
Diltiazem	Ritonavir	Tipranavir	
Elvitegravir and cobicistat and emtricitabine and tenofovir DF	Saquinavir	Verapamil	
Erythromycin	Telaprevir		
glecaprevir and pibrentasvir	Tipranavir		
Indinavir	Tucatinib		
Itraconazole	Verapamil		

Ketoconazole	Vonoprazan and amoxicillin and clarithromycin	
Lonafarnib	Voxilaprevir	
Sensitive OCT Substrates		
Imatinib		
Not an all-inclusive list.		

10.9. Appendix 9: Oral Solution or Suspension Palatability Questionnaire

1. Questionnaire should be administered to adult participants, preferably by a nurse.
2. Use colored copy of the Palatability Questionnaire.
3. Do not alter (reduce or enlarge) the original size of the Palatability Questionnaire.
4. Please collect the following background information:

Background Information

Study #/Study Site	
Period and Day	
Participant ID (Rand ID)	
Treatment	
Collect Date	
Collected By	
Entered in PIMS By	
Checked in PIMS By	
Questionnaire Fully Completed (circle one)	Yes/No

Please answer the following questions and provide a mark (X) on the color bar at approximately 1 (immediately), 5, 10 and 20 minutes after dosing. Please ensure participant has access to these descriptions when completing the questionnaire.

Q1: Mouth feel – Please tell us about the mouth feel (such as grittiness, stickiness, waxiness) of the product you tasted. Good represents normal mouth feel. Bad represents bad mouth feel.

Q2: Bitterness – Please tell us about the degree of bitterness of the product you tasted. Good represents not bitter at all. Bad represents extremely bitter.

Q3: Sweetness – Please tell us about the degree of sweet taste of the product you tasted. Good represents sweet. Bad represents not sweet at all.

Q4: Sourness – Please tell us about the degree of sour taste of the product you tasted. Good represents not sour at all. Bad represents extremely sour.

Q5: Saltiness – Please tell us about the degree of salty taste of the product you tasted. Good represents not salty at all. Bad represents extremely salty.

Q6: Tongue/mouth burn – Please tell us about the degree of tongue/mouth burn of the product you tasted. Good represents no burn at all. Bad represents extreme burn.

Q7: Overall liking – Please indicate how much you like or dislike the product you tasted. Good represents like. Bad represents dislike.

Details to assess questionnaire described below:

After the participants places the mark (X) on the color bar, the main Clinical Coordinator of the study and his back up or designee will procced follows:

① Measuring the total length of the bar on the printed questionnaire:

- Place the 30 cm study dedicated transparent ruler vertically at the top of the color bar (0 level over the green top bar) and measure the length till the end of the red bottom bar

② Measuring the placement of the “X” of the color bar of the printed questionnaire:

- Place the study dedicated transparent ruler at the top of the color bar and measure the length till the intersection point level of the “X” marked on the color bar

③ Entering data in PIMS

- Enter the the length of the whole bar (in mm) and measured distance to the point level of “X” (in mm) in PIMS according to each taste assessment undergone by each participant.
- Data will be Entered by/Checked by two different Clinical Coordinators (Main & Back up) or designee.

[figure not shown]
Example: How to provide a mark (X) on the color bar.

Within 1 minute (immediately) after dosing

[figure not shown]
Collection time:

Provide a mark (X) on the color bar.

[figure not shown]
5 minutes after dosing

Collection time: _____
Provide a mark (X) on the color bar.

[figure not shown]
10 minutes after dosing

Collection time:
Provide a mark (X) on the color bar.

20 minutes after dosing

Collection time: _____
Provide a mark (X) on the color bar.

Additional Feedback – After completing the “20 minute after dosing” palatability questions, please provide any additional descriptive feedback in the box below regarding the taste or odor of the drug.

10.10. Appendix 10: Abbreviations

The following is a list of abbreviations that may be used in the protocol.

Abbreviation	Term
% CV	percent coefficient of variation
A1 to A3	albuminuria (KDIGO albuminuria severity standardization)
Abs	absolute
ACR	albumin-to-creatinine ratio
ADL	activity/activities of daily living
AE	adverse event
AKI	acute kidney injury
ALP	alkaline phosphatase
ALT	alanine aminotransferase
API	active pharmaceutical ingredient
AST	aspartate aminotransferase
AUC	area under the curve
AUC ₁₂	area under the concentration-time curve from time 0 to 12 hours
AUC ₂₄	area under the concentration-time curve from time 0 to 24 hours
AUC _{tau}	area under the concentration-time curve at steady state over the dosing interval tau
AV	atrioventricular
AxMP	auxiliary medicinal product
BBS	Biospecimen Banking System
Bili	bilirubin
BID	twice-daily dosing
β-hCG	β-human chorionic gonadotropin
BMI	body mass index
BP	blood pressure
bpm	beats per minute
CFR	Code of Federal Regulations
CI	confidence interval
CIOMS	Council for International Organizations of Medical Sciences
CK	creatinine kinase
CKD-EPI	chronic kidney disease epidemiology
CL	total clearance of drug from eg, plasma
C _{max}	maximum observed concentration
CO ₂	carbon dioxide (bicarbonate)
COVID-19	coronavirus disease 2019
CRF	case report form
CRO	contract research organization
CRU	clinical research unit
CSR	Clinical Study Report
CT	clinical trial

Abbreviation	Term
CTCAE	Common Terminology Criteria for Adverse Events
CTIS	Clinical Trial Information System
CV	cardiovascular
CYP	cytochrome P450
DCT	data collection tool
DDI	drug-drug interaction
DIC	drug in capsule
DICI	drug-induced creatinine increase
DIKI	drug-induced kidney injury
DILI	drug-induced liver injury
DPB	dry powder blend
EC	ethics committee
ECC	emergency contact card
ECG	electrocardiogram or electrocardiography
eCrCl	estimated creatinine clearance
eCRF	electronic case report form
EDB	exposure during breastfeeding
E-DMC	External Data Monitoring Committee
EDP	exposure during pregnancy
EDR	extemporaneous dispensing record
eGFR	estimated glomerular filtration rate
EMA	European Medicines Agency
eSAE	electronic serious adverse event
EU	European Union
EudraCT	European Union Drug Regulating Authorities Clinical Trials (European Clinical Trials Database)
FSH	follicle-stimulating hormone
F/U	follow-up
GCP	Good Clinical Practice
GGT	gamma-glutamyl transferase
GI	gastrointestinal
HBP cyclodextrin	hydroxypropyl- β -cyclodextrin
HBsAg	hepatitis B surface antigen
HCVAb	hepatitis C antibody
HIV	human immunodeficiency virus
HR	heart rate
HRT	hormone replacement therapy
IB	Investigator's Brochure
ICD	informed consent document
ICH	International Council for Harmonisation of Technical Requirements for Pharmaceuticals for Human Use
ICU	intensive care unit
ID	identification

Abbreviation	Term
IMP	investigational medicinal product
IND	Investigational New Drug
INR	international normalized ratio
IPAL	Investigational Product Accountability Log
IRB	Institutional Review Board
KDIGO	Kidney Disease Improving Global Outcomes
LBBB	left bundle branch block
LFT	liver function test
LRTI	lower respiratory tract infection
MAD	multiple ascending dose
MATE	multidrug and toxin extrusion
MQI	medically qualified individual
MTD	maximum tolerated dose
NA	not applicable
NIMP	noninvestigational medicinal product
NOAEL	no observed adverse effect level
OAT	organic anion transporting
OATP	organic anion transporting polypeptide
OCT	organic cation transporter
PCRU	Pfizer Clinical Research Unit
PE	physical exam
P-gp	p-glycoprotein
PIMS	Phase 1 Management System
PK	pharmacokinetic(s)
PSSA	Pfizer's Serious Adverse Event Submission Assistant
PT	prothrombin time
PVC	premature ventricular contraction/complex
QTc	corrected QT interval
QTcF	QTc corrected using Fridericia's formula
qual	qualitative
RBC	red blood cell
ROA	route of administration
RSV	respiratory syncytial virus
SAD	single ascending dose
SAE	serious adverse event
SAP	Statistical Analysis Plan
Screat	serum creatinine
Scys	serum cystatin C
SD	standard deviation
SoA	schedule of activities
SOC	system organ class
SOP	standard operating procedure
SRSD	Single Reference Safety Document

Abbreviation	Term
SUSAR	Suspected Unexpected Serious Adverse Reaction
T bili	total bilirubin
TEAE	treatment emergent adverse event
THC	tetrahydrocannabinol
TI	therapeutic index
T _{max}	time to reach C _{max}
ULN	upper limit of normal
UACR	urine albumin-to-creatinine ratio
US	United States
USP	United States Pharmacopoeia
UTI	urinary tract infection
WBC	white blood cell
WOCBP	woman/women of childbearing potential

1. VERSION HISTORY

Table 1. Summary of Changes

Version/ Date	Associated Protocol Amendment	Rationale	Specific Changes
1 15 Aug 2023	Original 19 May 2023	N/A	N/A

2. INTRODUCTION

The purpose of this study is to perform palatability assessments to aid in the development of pediatric formulations of sisunatovir (PF-07923568).

This statistical analysis plan (SAP) provides the detailed methodology for summary and statistical analyses of the data collected in Study C5241014. This document may modify the plans outlined in the protocol; however, any major modifications of the primary endpoint definition or its analyses will also be reflected in a protocol amendment.

2.1. Modifications to the Analysis Plan Described in the Protocol

N/A

2.2. Study Objectives, Endpoints, and Estimands

There are no estimands for this study.

Type	Objective	Endpoint
Primary:		
Other	
 To assess the palatability attributes of sisunatovir in different formulations 	
 Palatability Assessment Questionnaire Scoring Metrics: mouth feel, bitterness, sweetness, sourness, saltiness, tongue/mouth burn, overall liking
Secondary:		
Safety	
 To assess safety and tolerability following oral administration of each sisunatovir formulations 	
 Assessment of TEAEs, clinical laboratory abnormalities and vital signs

2.3. Study Design

This is a single-blind, randomized, multi-period study in healthy male and/or female adult participants. Approximately 12 participants will assess the palatability attributes of a total of

6 formulations (Formulations A to F) over 2 days in a crossover manner. There will be a maximum of 4 periods each day, and one formulation will be administered at each period for tasting in a blinding fashion, except on Day 2 where there will be one period with no administration. A minimum of 3 participants from each gender is required.

All participants will be discharged on Day 2 after completion of all required assessments. If the participant accidentally ingests the taste sample containing the active ingredient, he/she will not be permitted to continue evaluating any further taste samples and will be withdrawn from the study.

Participants who discontinue from the study may be replaced at the sponsor's discretion. The replacement participant will receive the same treatment sequences as the participant who discontinued.

The study sample dosing scheme is shown below in Figure 1.

Figure 1. Sample Dosing Scheme

	Session 1 (Day 1)				Session 2 (Day 2)			
	Period 1	Period 2	Period 3	Period 4	Period 5	Period 6	Period 7	Period 8
N=3	A	B	D	C	A	E	No	F
N=3	B	C	A	D	E	F	A	No
N=3	C	D	B	A	F	No	E	A
N=3	D	A	C	B	No	A	F	E

Treatment A: CCI mg/mL Sisunatovir CCI
 Treatment B: CCI mg/mL Sisunatovir, CCI

Treatment C: CCI

Treatment D: CCI mg/mL Sisunatovir and CCI

Treatment E: CCI mg/mL Sisunatovir and CCI

Treatment F: CCI mg/mL Sisunatovir, CCI

No: No administration and indicated as 'X' in randomization

Note CCI

3. ENDPOINTS AND BASELINE VARIABLES: DEFINITIONS AND CONVENTIONS

3.1. Primary Endpoint(s)

3.1.1. Palatability Assessment Questionnaire Scoring Metrics: mouth feel, bitterness, sweetness, sourness, saltiness, tongue/mouth burn, overall liking

Participants will swirl the sample in the mouth for approximately 10 seconds, and then spit it out. Participants will assess various aspects of the taste, including mouth feel, bitterness, sweetness, sourness, saltiness, tongue/mouth burn, and overall liking using the Oral Solution or Suspension Palatability Questionnaire (Appendix 2).

Palatability assessments will be carried at approximately 1 minute, 5 minutes, 10 minutes, and 20 minutes after dosing.

The data collected for palatability assessment using the sponsor-provided palatability questionnaire will be numerically derived by measuring length (using a scale with gradations of at least 0.1 cm) of the 'x' marked by the participant relative to the 'good trait'. For palatability assessment, the data used in the analysis will be transcribed and rescaled to a score from 0 to 100 from the raw measurements on the questionnaire.

3.2. Secondary Endpoint(s)

As listed in [Section 2.2](#), the secondary endpoint is related to the safety/tolerability of oral administration of sisunatovir and is described in [Section 3.5](#).

3.3. Other Endpoint(s)

N/A

3.4. Baseline Variables

N/A

3.5. Safety Endpoints

The following data will be considered in standard safety summaries (see protocol for collection times, baseline assessment, and list of parameters):

- Adverse events (AE)
- Clinical laboratory assessments
- Vital signs
- Electrocardiograms

3.5.1. Adverse Events

Any adverse events occurring following start of treatment will be considered as treatment-emergent adverse events (TEAE). If an AE starts on the same day as the first dose date, it will be considered treatment-emergent unless the CRF data indicates otherwise via explicitly recording time for AE onset which has occurred before the first treatment dosing. Events that occur during follow-up within the lag time of up to 28-35 days after the last dose of study intervention will be counted as treatment-emergent and attributed to the last treatment taken. Events that occur during the washout period between treatments will be counted as treatment-emergent and attributed to the previous treatment taken. The time period for collecting AEs (“active collection period”) for each participant begins from the time the participant provides informed consent. The algorithm will not consider any events that started prior to the first dose date.

A 3-tier approach for summarizing adverse events (AEs) will not be used due to the low number of participants planned to be recruited.

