1.2. Schema

Table 1. Sample Dosing Scheme

	Session 1 (Day 1)				Session 2 (Day 2)			
	Period 1	Period 2	Period 3	Period 4	Period 5	Period 6	Period 7	Period 8
N=3	A	B	D	C	A	E	No	F
N=3	B	C	A	D	E	F	A	No
N=3	C	D	B	A	F	No	E	A
N=3	D	A	C	B	No	A	F	E

Treatment A: CCI mg/mL Sisunatovir CCI
Treatment B: [REDACTED] mg/mL Sisunatovir, CCI
[REDACTED]
Treatment C: CCI [REDACTED]
Treatment D: CCI mg/mL Sisunatovir and CCI
Treatment E: [REDACTED] mg/mL Sisunatovir and [REDACTED]
Treatment F: [REDACTED] mg/mL Sisunatovir, CCI
[REDACTED]
[REDACTED]
No: No administration and indicated as 'X' in randomization
Note: CCI
[REDACTED]

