3. OBJECTIVES AND ENDPOINTS

Objectives	Endpoints
Primary: 
To assess the palatability attributes of sisunatovir in different formulations	Primary: 
Palatability Assessment Questionnaire Scoring Metrics: mouth feel, bitterness, sweetness, sourness, saltiness, tongue/mouth burn, overall liking.
Secondary: 
To assess safety and tolerability following oral administration of each sisunatovir formulations	Secondary: 
Assessment of TEAEs, clinical laboratory abnormalities and vital signs.

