9.3.1. General Considerations

Details of the analyses will be provided in the Statistical Analysis Plan. All treatment arms will be reported separately.

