5.2. General Methods

Descriptive analyses will be performed, and some measures will be summarized using graphical representations

The analyses related to the primary and secondary endpoints will be based on the appropriate population for analysis (see [Section 4](#)).

Unless otherwise stated, all summaries and plots will be presented by treatment group. The following treatment group labels (or similar) will be used:

- Treatment A: **CCI** mg/mL Sisunatovir **CCI**

- Treatment B: **CCI** mg/mL Sisunatovir, **CCI**
- Treatment C: **CCI**
- Treatment D: **CCI** mg/mL Sisunatovir and **CCI**
- Treatment E: **CCI** mg/mL Sisunatovir and **CCI**
- Treatment F: **CCI** mg/mL Sisunatovir, **CCI**

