6.5.1. Adverse Events

Adverse events will be reported in accordance with the sponsor reporting standards.

Participant discontinuations due to adverse events will be detailed by treatment, where appropriate. Data will be reported in accordance with the sponsor reporting standards.

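### SAP 3.5.1 credits all follow-up TEAEs to the last product tasted, which under the sample scheme is A, E or F for every completer and never B, C or D (minor reporting point)

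*SAP*

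**What the plan says.** SAP 3.5.1 has two attribution rules. For the follow-up lag of up to 28-35 days after the last dose, events "will be counted as treatment-emergent and attributed to the last treatment taken". For the gaps between tastings, "Events that occur during the washout period between treatments will be counted as treatment-emergent and attributed to the previous treatment taken".

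The order of tasting is in Protocol 1.2, under the title "Table 1. Sample Dosing Scheme". SAP 2.3 repeats it ("The study sample dosing scheme is shown below in Figure 1"). The two grids are identical. Products A to D are tasted on Day 1. Day 2 holds A again, E, F and one empty period.

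The secondary objective in Protocol 3 is "To assess safety and tolerability following oral administration of each sisunatovir formulations". On presentation, Protocol 9.3.1 states "All treatment arms will be reported separately" and SAP 5.2 states "Unless otherwise stated, all summaries and plots will be presented by treatment group". The AE section itself, SAP 6.5.1, gives no layout: "Adverse events will be reported in accordance with the sponsor reporting standards". It adds only that discontinuations due to AEs are detailed by treatment where appropriate. The SAP has no separate category for follow-up events.

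**The concern.** Attributing an event to the most recent treatment makes sense when each period is long relative to the effect being attributed. Here the tastings on a day may be as little as 60 minutes apart (Protocol 6.1.1), and a follow-up of four to five weeks comes after the last one. An event in week three then carries no information about which of six products, all tasted within two days, might be responsible. The rule still names one.

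Investigator causality does not settle it. Protocol 10.3.3 asks for the relationship to study intervention, which Protocol 6 defines as sisunatovir and not as a particular formulation.

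At stake is how the by-formulation safety table reads. If all six products were equally well tolerated, late events among completers would still add to A, E and F and never to B, C or D. A reader could take the empty follow-up contribution for B, C and D as better tolerability.

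**Working it through.** **Inputs.** Four sequences with three participants each (Protocol Table 1, SAP Figure 1); 12 participants to be randomized (Protocol 9.5); attribution rules from SAP 3.5.1. An empty period cannot be the last treatment.

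**Check on the total.** 4 × 3 = 12, which matches Protocol 9.5.

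**Last product tasted, by sequence**

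| Day 1 | Day 2 | Last on Day 1 | Last overall | n |
|---|---|---|---|---|
| A B D C | A E – F | C | F | 3 |
| B C A D | E F A – | D | A | 3 |
| C D B A | F – E A | A | A | 3 |
| D A C B | – A F E | B | E | 3 |

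**Follow-up credit among 12 completers.** A 3 + 3 = 6 (50%), E 3 (25%), F 3 (25%), B, C and D 0.

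**Exposure does not explain the split.** A is tasted twice by everyone (24 tastings) and the other five once (12 each), 84 in all. A's share of tastings is 24/84 = 28.6% and each other product's is 12/84 = 14.3%, against follow-up shares of 50% for A, 25% each for E and F, and 0% for B, C and D.

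**Time governed by the rule.** Follow-up is 12 × 28 = 336 to 12 × 35 = 420 person-days, against at most 12 × 2 = 24 on the tasting days. So at least 336/(336 + 24) = 93% of treatment-emergent observation time falls under the last-treatment rule.

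**Size in the table.** The documents give no AE rate, so the rates below are assumptions. Let r be the share of participants with a follow-up-onset TEAE, equal for everyone and unrelated to formulation. Expected participants credited are 6r for A, 3r each for E and F, and 0 for B, C and D. The chance of at least one such participant is 1 − (1 − r)^12.

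| Assumed r | Expected total | A | E | F | B, C, D | Chance of at least one |
|---|---|---|---|---|---|---|
| 0% | 0 | 0 | 0 | 0 | 0 | 0% |
| 5% | 0.6 | 0.30 | 0.15 | 0.15 | 0 | 46% |
| 10% | 1.2 | 0.60 | 0.30 | 0.30 | 0 | 72% |
| 25% | 3.0 | 1.50 | 0.75 | 0.75 | 0 | 97% |

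With all 12 tasting every product, r = 10% would add 0.60/12 = 5.0% to A, 0.30/12 = 2.5% each to E and F, and nothing to B, C or D.

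**Overnight check.** The last Day 1 products are C, D, A and B, so overnight credit is 3 each for A, B, C and D. E and F get none, correctly, because nobody has tasted them yet.

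**Scheduled postdose assessments.** The only planned postdose laboratory tests, ECG and vital signs come after the final palatability assessment on Day 2 (Protocol 1.3). Under Protocol 10.3.1 a clinically significant abnormality can be an AE. If its onset is set at that assessment, in a completer it too falls under A, E or F.

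**The case against.** The strongest reply is that this hardly matters. The study is descriptive, no hypothesis is tested and no decision rule uses the TEAE table. Samples are spat out and Protocol 4.3 expects no appreciable absorption. Protocol 2.2.4 describes a low occurrence of related TEAEs in healthy adults. All of this stands and sets the severity. It does not remove the artefact, because TEAEs are counted whatever their cause.

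The rule is also prespecified and applied alike to everyone, and it works in one important case. A participant who accidentally ingests an active sample stops tasting and is withdrawn (Protocol 4.1, 6.5), so the last treatment is the ingested product and later events are credited to it. This stands, and the rule should be kept there.

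The sponsor standards cited in SAP 6.5.1 may already include an Overall column. That is possible, but SAP 3.5.1 states the attribution explicitly and nothing else in the SAP overrides it.

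Three stronger readings are tempting and are not supported:

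- *Overnight attribution is biased as well.* It is not: credit is balanced across the four products tasted by then.
- *B, C and D can show no TEAEs.* They can, from events between tastings, from the first night, and from participants who stop on Day 1.
- *Three sisunatovir formulations lose their late events.* Treatment C's label is redacted, so C may not be a sisunatovir formulation and may lie outside the secondary objective.

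Nor is same-day attribution secure. With Tmax at 5-6 hours (Protocol 2.2.4) and tastings possibly an hour apart, a systemic event need not come from the product just tasted. That rule is a convention, most informative for immediate local effects.

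**Conclusion.** The point holds as a minor reporting defect. Among completers, follow-up TEAEs would be credited 6:3:3 to A, E and F and never to B, C or D, for reasons of schedule only. The practical effect is none to a few table entries.

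This rests on four conditions:

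- The scheme is labelled a sample. The zero for B, C and D needs only that they stay on Day 1 in the final randomization; the 6:3:3 split also needs the Day 2 orders as shown.
- The counts apply to completers, three per sequence. Replacements take the same sequence as the participant replaced (Protocol 4.1), which preserves the split if they complete.
- TEAE reporting by treatment is inferred from SAP 5.2 and Protocol 9.3.1, since SAP 6.5.1 leaves the layout to sponsor standards that are not in the documents.
- The event rates in the calculation are illustrative.

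A reader might infer that the safety objective is compromised. The documents do not support that: events close to a tasting are still assigned to it, and individual late events can still be reported.

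**What to change.** Amend SAP 3.5.1 and 6.5.1 as follows.

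1. For participants who completed the tastings, show TEAEs with onset after the Day 2 session in a separate column, *follow-up, not attributable to a single formulation*, and not under the last product. Define session end as a prespecified interval after the last tasting, with the length chosen by the sponsor, so that acute events after that tasting stay with it.
2. Include an Overall column.
3. State in the same rule how AEs arising from the end-of-Day-2 laboratory, ECG and vital-sign assessments are classified.
4. Keep the last-treatment rule for participants withdrawn early, including after accidental ingestion, so that their later events stay with the last (ingested) product. Say explicitly that ingestion at the final tasting counts here and not under item 1.
5. Keep the washout rule, with a footnote that attribution between tastings is by convention and is most informative for immediate local effects.

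The cost is SAP wording, one or two table columns, and fewer events shown under individual formulations. Onset times are needed on Day 2 to apply the session end. Dose times are already recorded (Protocol 6.5), and SAP 3.5.1 already refers to recorded onset times. Design, sample size and conduct do not change.
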